#### Weight:

4. BMI of 17.5 to 30.5 kg/m^2; and a total body weight >50 kg (110 lb).

#### **Informed Consent:**

5. Capable of giving signed informed consent as described in Appendix 1, which includes compliance with the requirements and restrictions listed in the ICD and in this protocol.

#### 5.2. Exclusion Criteria

Participants are excluded from the study if any of the following criteria apply:

#### **Medical Conditions:**

- 1. Evidence or history of clinically significant hematological, renal, endocrine, pulmonary, gastrointestinal, cardiovascular, hepatic, psychiatric, neurological, or allergic disease (including drug allergies, but excluding untreated, asymptomatic, seasonal allergies at the time of dosing).
- 2. Any condition possibly affecting drug absorption (eg, gastrectomy).
- 3. History of HIV infection, hepatitis B, or hepatitis C; positive testing for HIV, HBsAg, HBcAb or HCVAb. Hepatitis B vaccination is allowed.
- 4. Other medical or psychiatric condition including recent (within the past year) or active suicidal ideation/behavior or laboratory abnormality or other conditions or

situations related to COVID-19 pandemic (eg. Contact with positive case, residence, or travel to an area with high incidence) that may increase the risk of study participation or, in the investigator's judgment, make the participant inappropriate for the study.

#### **Prior/Concomitant Therapy:**

- 5. Use of prescription or nonprescription drugs and dietary and herbal supplements within 7 days or 5 half-lives (whichever is longer) prior to the first dose of study intervention. (Refer to Section 6.8 Concomitant Therapy for additional details).
- 6. Current use of any prohibited concomitant medication(s) or those unwilling/unable to use a permitted concomitant medication(s). Refer to Section 6.8 Concomitant Therapy.

#### **Prior/Concurrent Clinical Study Experience:**

7. Previous administration with an investigational drug within 30 days (or as determined by the local requirement) or 5 half-lives preceding the first dose of study intervention used in this study (whichever is longer).

#### **Diagnostic Assessments:**

- 8. A positive urine drug test.
- 9. Screening supine BP ≥140 mm Hg (systolic) or ≥90 mm Hg (diastolic), following at least 5 minutes of supine rest. If BP is ≥140 mm Hg (systolic) or ≥90 mm Hg (diastolic), the BP should be repeated 2 more times and the average of the 3 BP values should be used to determine the participant's eligibility.
- 10. Baseline standard 12-lead ECG that demonstrates clinically relevant abnormalities that may affect participant safety or interpretation of study results (eg, baseline QTcF interval >450 msec, complete LBBB, signs of an acute or indeterminate- myocardial infarction, ST interval and T-wave changes suggestive of myocardial ischemia, second or third-degree AV block, or serious bradyarrhythmias or tachyarrhythmias). If the baseline uncorrected QT interval is >450 msec, this interval should be rate--corrected using the Fridericia method and the resulting QTcF should be used for decision making and reporting. If QTcF exceeds 450 msec, or QRS exceeds 120 msec, the ECG should be repeated 2 more times and the average of the 3 QTcF or QRS values should be used to determine the participant's eligibility. Computer-interpreted ECGs should be overread by a physician experienced in reading ECGs before excluding a participant.

- 11. Participants with ANY of the following abnormalities in clinical laboratory tests at screening, as assessed by the study-specific laboratory and confirmed by a single repeat test, if deemed necessary:
  - AST or ALT level ≥1.5 × ULN;
  - Total bilirubin level ≥1.5 × ULN; participants with a history of Gilbert's syndrome may have direct bilirubin measured and would be eligible for this study provided the direct bilirubin level is≤ ULN.

#### **Other Exclusions:**

- 12. History of alcohol abuse or binge drinking and/or any other illicit drug use or dependence within 6 months of Screening. Binge drinking is defined as a pattern of 5 (male) and 4 (female) or more alcoholic drinks in about 2 hours. As a general rule, alcohol intake should not exceed 14 units per week (1 unit = 8 ounces (240 mL) beer, 1 ounce (30 mL) of 40% spirit or 3 ounces (90 mL) of wine).
- 13. Blood donation (excluding plasma donations) of approximately 1 pint (500 mL) or more within 60 days prior to dosing.
- 14. Use of tobacco- or nicotine-containing products in excess of the equivalent of 5 cigarettes per day. For chewing tobacco, one chew is equivalent to approximately 2-3 cigarettes, so participants would be limited to 2 or less chews per day.
- 15. History of sensitivity to prazosin hydrochloride or any of the components in the formulation of the study products.
- 16. Unwilling or unable to comply with the criteria in the Lifestyle Considerations section of this protocol.
- 17. Investigator site staff or Pfizer employees directly involved in the conduct of the study, site staff otherwise supervised by the investigator, and their respective family members.

#### 5.3. Lifestyle Considerations

The following guidelines are provided:

#### 5.3.1. Meals and Dietary Restrictions

- Participants must abstain from all food and drink (except water) at least 4 hours prior to any safety laboratory evaluations and 10 hours prior to the collection of the predose PK sample.
- Water is permitted until 1 hour prior to study intervention administration. Water may be consumed without restriction beginning 1 hour after dosing. Noncaffeinated drinks

(except grapefruit or grapefruit-related citrus fruit juices—see below) may be consumed with meals and the evening snack.

- Lunch will be provided approximately 4 hours after dosing.
- Dinner will be provided approximately 9 to 10 hours after dosing.
- An evening snack may be permitted.
- Participants will refrain from consuming red wine, grapefruit, or grapefruit-related citrus fruits (eg, Seville oranges, pomelos, fruit juices) from 7 days prior to the first dose of study intervention until collection of the final PK blood sample.
- While participants are confined, their total daily nutritional composition should be approximately 55% carbohydrate, 30% fat, and 15% protein. The daily caloric intake per participant should not exceed approximately 3200 kcal.

#### 5.3.2. Caffeine, Alcohol, and Tobacco

- Participants will abstain from caffeine-containing products for 24 hours prior to the start of dosing until collection of the final PK sample of each study period.
- Participants will abstain from alcohol for 24 hours prior to admission to the clinical research unit (CRU) and continue abstaining from alcohol until collection of the final PK sample of each study period. Participants may undergo an alcohol breath test or blood alcohol test at the discretion of the investigator.
- Participants will abstain from the use of tobacco- or nicotine-containing products for 24 hours prior to dosing and during confinement in the CRU.

#### 5.3.3. Activity

- Participants will abstain from strenuous exercise (eg, heavy lifting, weight training, calisthenics, aerobics) for at least 48 hours prior to each blood collection for clinical laboratory tests. Walking at a normal pace will be permitted;
- In order to standardize the conditions on PK sampling days, participants will be required to refrain from lying down (except when required for BP, pulse rate, and ECG measurements), eating, and drinking beverages other than water during the first 4 hours after dosing;
- If participant is laying down, to avoid the situation of sudden hypotension and dizziness, he/she should stand up gradually such as sitting before standing up.

#### **5.3.4.** Contraception

The investigator or his or her designee, in consultation with the participant, will confirm that the participant has selected an appropriate method of contraception for the individual participant and his or her partner(s) from the permitted list of contraception methods (see Appendix 4 Section 10.4.4) and will confirm that the participant has been instructed in its consistent and correct use. At time points indicated in the SoA, the investigator or designee will inform the participant of the need to use highly effective contraception consistently and correctly and document the conversation and the participant's affirmation in the participant's chart (participants need to affirm their consistent and correct use of at least 1 of the selected methods of contraception) considering that their risk for pregnancy may have changed since the last visit. In addition, the investigator or designee will instruct the participant to call immediately if the selected contraception method is discontinued or if pregnancy is known or suspected in the participant or partner.

#### 5.4. Screen Failures

Screen failures are defined as participants who consent to participate in the clinical study but are not subsequently randomly assigned to study intervention. Screen failure data are collected and remain as source and are not reported on the CRF.

Individuals who do not meet the criteria for participation in this study (screen failure) may not be rescreened.

#### 6. STUDY INTERVENTION(S) AND CONCOMITANT THERAPY

Study intervention is defined as any investigational intervention(s), marketed product(s), placebo, medical device(s), or study procedure(s) intended to be administered to a study participant according to the study protocol.

For the purposes of this protocol, study intervention refers to investigational product.

#### 6.1. Study Intervention(s) Administered

For the purposes of this protocol, study intervention refers to prazosin HCl capsules.

Prazosin HCl 2 mg and 5 mg capsules, manufactured at Pfizer Pharmaceutical, Barceloneta, Puerto Rico and prazosin HCl 1 mg, 2 mg and 5 mg capsules, manufactured at Pfizer Pharmaceutical, Ascoli, Italy will be supplied to the CRU along with individual dosing containers for unit dosing.

Pivotal BE study capsules will be supplied to the CRU in multidose labeled containers (in sufficient number to allow unopened containers to be kept as retains).

#### 6.1.1. Administration

Following an overnight fast of at least 10 hours, participants will receive study intervention at approximately 0800 hours (plus or minus 2 hours). Investigator site personnel will administer study intervention during each period with ambient temperature water to a total

volume of approximately 240 mL. Participants will swallow the study intervention whole, and will not manipulate or chew the study intervention prior to swallowing.

In order to standardize the conditions on PK sampling days, all participants will be required to refrain from lying down (except when required for BP, pulse rate, and ECG measurements), eating, and drinking beverages other than water during the first 4 hours after dosing.

#### 6.2. Preparation, Handling, Storage, and Accountability

- 1. The investigator or designee must confirm appropriate temperature conditions have been maintained during transit for all study interventions received and any discrepancies are reported and resolved before use of the study intervention.
- 2. Only participants enrolled in the study may receive study intervention and only authorized site staff may supply or administer study intervention. All study interventions must be stored in a secure, environmentally controlled, and monitored (manual or automated recording) area in accordance with the labeled storage conditions with access limited to the investigator and authorized site staff. At a minimum, daily minimum and maximum temperatures for all site storage locations must be documented and available upon request. Data for nonworking days must indicate the minimum and maximum temperatures since previously documented for all site storage locations upon return to business.
- 3. Any excursions from the study intervention label storage conditions should be reported to Pfizer upon discovery along with any actions taken. The site should actively pursue options for returning the study intervention to the storage conditions described in the labeling, as soon as possible. Once an excursion is identified, the study intervention must be quarantined and not used until Pfizer provides permission to use the study intervention. Specific details regarding the definition of an excursion and information the site should report for each excursion will be provided to the site in the IP manual.
- 4. Any storage conditions stated in the SRSD will be superseded by the storage conditions stated on the label.
- 5. Study interventions should be stored in their original containers.
- 6. The investigator, institution, or the head of the medical institution (where applicable) is responsible for study intervention accountability, reconciliation, and record maintenance (ie, receipt, reconciliation, and final disposition records), such as the IPAL or sponsor-approved equivalent. All study interventions will be accounted for using a study intervention accountability form/record.
- 7. Further guidance and information for the final disposition of unused study interventions are provided in the IP manual. All destruction must be adequately documented. If destruction is authorized to take place at the investigator site, the

investigator must ensure that the materials are destroyed in compliance with applicable environmental regulations, institutional policy, and any special instructions provided by Pfizer

8. All pivotal BE retained capsules should be stored by the investigator site or with a third-party vendor. Sample retention is the responsibility of the entity performing the BE study.

Upon identification of a product complaint, notify the sponsor within 1 business day of discovery.

#### 6.2.1. Preparation and Dispensing

Within this protocol, preparation refers to the investigator site activities performed to make the study intervention ready for administration or dispensing to the participant by qualified staff. Dispensing is defined as the provision of study intervention, concomitant treatments, and accompanying information by qualified staff member(s) to a healthcare provider, participant in accordance with this protocol. Local health authority regulations or investigator site guidelines may use alternative terms for these activities.

Capsules will be prepared at the CRU in the individual dosing containers by 2 operators, 1 of whom is an appropriately qualified and experienced member of the study staff (eg, physician, nurse, physician's assistant, nurse practitioner, pharmacy assistant/technician, or pharmacist). The capsules will be provided in unit dose containers and labeled in accordance with Pfizer regulations and the clinical site's labeling requirements.

#### 6.3. Measures to Minimize Bias: Randomization and Blinding

#### 6.3.1. Allocation to Study Intervention

The investigator's knowledge of the treatment should not influence the decision to enroll a particular participant or affect the order in which participants are enrolled.

The investigator will assign participant numbers to the participants as they are screened for the study. Pfizer will provide a randomization schedule to the investigator and, in accordance with the randomization numbers, the participant will receive the study treatment regimen assigned to the corresponding randomization number.

#### 6.4. Study Intervention Compliance

When participants are dosed at the site, they will receive study intervention directly from the investigator or designee, under medical supervision. The date and time of each dose administered in the clinic will be recorded in the source documents and recorded in the CRF. The dose of study intervention and study participant identification will be confirmed at the time of dosing by a member of the study site staff other than the person administering the study intervention. Study site personnel will examine each participant's mouth to ensure that the study intervention was ingested.

#### 6.5. Dose Modification

Does modification is not applicable to this study.

#### 6.6. Continued Access to Study Intervention After the End of the Study

No intervention will be provided to study participants at the end of their study participation.

#### **6.7. Treatment of Overdose**

For this study, any dose of study intervention greater than 5 mg within a 24-hour time period will be considered an overdose.

The sponsor does not recommend specific treatment for an overdose.

In the event of an overdose, the investigator should:

- 1. Contact the medical monitor within 24 hours.
- 2. Closely monitor the participant for any AEs/SAEs and laboratory abnormalities for at least 5 half-lives or 28 calendar days after the overdose of study intervention (whichever is longer).
- 3. Document the quantity of the excess dose as well as the duration of the overdose in the CRF.
- 4. Overdose is reportable to Pfizer Safety only when associated with an SAE.
- 5. Obtain a blood sample for PK analysis within 1 day from the date of the last dose of study intervention if requested by the medical monitor (determined on a case-by-case basis).

Decisions regarding dose interruptions or modifications will be made by the investigator in consultation with the medical monitor based on the clinical evaluation of the participant.

#### **6.8.** Concomitant Therapy

Use of prescription or nonprescription drugs and dietary and herbal supplements are prohibited within 7 days or 5 half-lives (whichever is longer) prior to the first dose of study intervention. Limited use of nonprescription medications that are not believed to affect participant safety or the overall results of the study may be permitted on a case-by-case basis following approval by the sponsor. Acetaminophen/paracetamol may be used at doses of ≤1 g/day.

Females using hormonal contraceptives or taking hormone replacement therapy may be eligible to participate in this study if they are willing to discontinue therapy at least 28 days prior to the first dose of study treatment and remain off hormonal therapy for the duration of the study. Depo-Provera® must be discontinued at least 6 months prior to the first dose of study treatment.

All concomitant treatments taken during the study must be recorded with indication, daily dose, and start and stop dates of administration. All participants will be questioned about concomitant treatment at each clinic visit.

Treatments taken within 28 days before the first dose of study intervention will be documented as a prior treatment. Treatments taken after the first dose of study intervention will be documented as concomitant treatments.

# 7. DISCONTINUATION OF STUDY INTERVENTION AND PARTICIPANT DISCONTINUATION/WITHDRAWAL

#### 7.1. Discontinuation of Study Intervention

It may be necessary for a participant to permanently discontinue study intervention. Reasons for permanent discontinuation of study intervention include the following

- significant change in vital signs or
- adverse event.

If study intervention is permanently discontinued, the participant will not remain in the study for further evaluation. See the SoA for data to be collected at the time of discontinuation of study intervention.

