#### 7.2. Participant Discontinuation/Withdrawal From the Study

A participant may withdraw from the study at any time at his/her own request. Reasons for discontinuation from the study include the following:

- Refused further study procedures;
- Lost to follow-up;
- Death:
- Study terminated by sponsor;

At the time of discontinuing from the study, if possible, an early discontinuation visit should be conducted. See the SoA for assessments to be collected at the time of study discontinuation and follow-up and for any further evaluations that need to be completed.

The early discontinuation visit applies only to participants who are enrolled/randomized and then are prematurely withdrawn from the study. Participants should be questioned regarding their reason for withdrawal.

The participant will be permanently discontinued from the study intervention and the study at that time.

If a participant withdraws from the study, he/she may request destruction of any remaining samples taken and not tested, and the investigator must document any such requests in the site study records and notify the sponsor accordingly.

If the participant withdraws from the study and also withdraws consent (see Section 7.2.1) for disclosure of future information, no further evaluations should be performed and no additional data should be collected. The sponsor may retain and continue to use any data collected before such withdrawal of consent.

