#### 7.2.1. Withdrawal of Consent

Participants who request to discontinue receipt of study intervention will remain in the study and must continue to be followed for protocol-specified follow-up procedures. The only exception to this is when a participant specifically withdraws consent for any further contact with him or her or persons previously authorized by the participant to provide this information. Participants should notify the investigator in writing of the decision to withdraw consent from future follow--up, whenever possible. The withdrawal of consent should be explained in detail in the medical records by the investigator, as to whether the withdrawal is only from further receipt of study intervention or also from study procedures and/or posttreatment study follow--up, and entered on the appropriate CRF page. In the event that vital status (whether the participant is alive or dead) is being measured, publicly available information should be used to determine vital status only as appropriately directed in accordance with local law.

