## 8.3.1. Time Period and Frequency for Collecting AE and SAE Information

The time period for actively eliciting and collecting AEs and SAEs ("active collection period") for each participant begins from the time the participant provides informed consent, which is obtained before the participant's participation in the study (ie, before undergoing any study-related procedure and/or receiving study intervention), through and including a minimum of 28 calendar days after the last administration of the study intervention.

Follow-up by the investigator continues throughout and after the active collection period and until the AE or SAE or its sequelae resolve or stabilize at a level acceptable to the investigator.

For participants who are screen failures, the active collection period ends when screen failure status is determined.

If the participant withdraws from the study and also withdraws consent for the collection of future information, the active collection period ends when consent is withdrawn.

If a participant permanently discontinues or temporarily discontinues study because of an AE or SAE, the AE or SAE must be recorded on the CRF and the SAE reported using the CT SAE Report Form.

Investigators are not obligated to actively seek information on AEs or SAEs after the participant has concluded study participation. However, if the investigator learns of any SAE, including a death, at any time after a participant has completed the study, and he/she considers the event to be reasonably related to the study intervention, the investigator must promptly report the SAE to Pfizer using the CT SAE Report Form.

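### Section 7.1 takes participants whose dosing is permanently stopped out of the study, while 8.3.1, 8.3.3 and the Schedule of Activities still require their adverse events to be collected and followed

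*Protocol*

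**What the plan says.** **Protocol 7.1** gives reasons for permanent discontinuation of study intervention that include "significant change in vital signs or" an adverse event. It continues that, once dosing is permanently stopped, "the participant will not remain in the study for further evaluation". The next sentence adds: "See the SoA for data to be collected at the time of discontinuation of study intervention".

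**Protocol 7.2.1** says: "Participants who request to discontinue receipt of study intervention will remain in the study and must continue to be followed for protocol-specified follow-up procedures". Its only exception is a participant who withdraws consent to any further contact.

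**Protocol 8.3.1** runs the active collection period for AEs and SAEs, for each participant, from consent "through and including a minimum of 28 calendar days after the last administration of the study intervention". It names two early ends: determination of screen failure, and withdrawal from the study together with withdrawn consent for future information. It also deals with participants who discontinue because of an AE, asking that the event be recorded and any SAE reported, and it does not shorten their window. Separately, it relieves investigators of actively seeking events once a participant has concluded participation.

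**Protocol 8.3.3** requires proactive follow-up of each participant after an AE report, until the event resolves, stabilises or is otherwise explained, or the participant is lost to follow-up.

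**SoA (Table 1)** has an early termination/discontinuation column and a follow-up column. Note g makes the follow-up contact mandatory 28 to 35 days after the final dose and allows it by telephone.

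**The concern.** Section 7.1 attaches leaving the study to permanent discontinuation of dosing, and the reasons it lists are safety reasons. Taken at its word, it ends a participant's time in the study at the moment a safety event has stopped dosing. Sections 8.3.1 and 8.3.3 and SoA note g expect that same participant to be followed for about another month.

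What is at stake is the completeness of the safety data and the oversight of the participants concerned. Safety and tolerability is the only stated secondary objective, and AEs are one of its endpoints. The participants are healthy volunteers for whom the protocol expects no clinical benefit. The risks it lists for prazosin (dizziness, weakness and palpitations among them) are of the kind that could lead to a stop under 7.1. If sites read 7.1 differently, later events and the resolution of earlier ones could be recorded for some of these participants and not for others.

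**Working it through.** The main check is to set the rules side by side. Simple day counts then give the size.

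**1. Who 7.1 covers.** The sentence on leaving the study is conditional only on permanent discontinuation of study intervention. It has no exception, and it points to the SoA only for data due at the time of discontinuation, not afterwards.

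**2. 7.1 against 8.3.1.** 8.3.1 applies to each participant and closes the window early in two cases only. A stop for an AE or a vital-sign change is neither. One section says the participant is no longer in the study for evaluation; the other requires active collection for at least 28 more days. This is the direct conflict.

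**3. 7.1 against SoA note g and 8.3.3.** Note g requires the contact and exempts no one who stopped dosing early. 8.3.3 requires follow-up at subsequent visits or contacts, which assumes that these take place.

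**4. 7.1 against 7.2.1.** The wording is opposed: not remaining in the study against remaining in it. The situations overlap only in part, because 7.2.1 concerns participants who ask to stop. Someone who asks to stop because of an AE falls under both.

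**5. Does another rule settle the matter?** No. 8.3.1 lifts the duty to seek events once participation has concluded, and 7.1 can be read as saying that it has. No section says which passage prevails.

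**6. The plan's own schedule.** Protocol 4.1 gives about 6 weeks from screening to discharge and about 11 weeks to follow-up. Inputs: screening up to 28 days, washout at least 7 days, discharge one day after the last dose, contact 28 to 35 days after the last dose.

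- Cohort 1: last dose at 28 + 2 × 7 = day 42. Discharge at day 43, and 43 / 7 = 6.1 weeks. Contact at 42 + 28 = day 70 to 42 + 35 = day 77, that is 10.0 to 11.0 weeks.
- Cohort 2: last dose at 28 + 7 = day 35. Discharge at day 36, and 36 / 7 = 5.1 weeks. Contact at day 63 to day 70, that is 9.0 to 10.0 weeks.

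The stated 6 and 11 weeks are reproduced by Cohort 1 with full screening and the 28-35 day contact. The planned length of participation therefore includes that contact.

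**7. Days left uncovered if 7.1 is followed literally.** Let d be the day of exit after the last dose. The documents do not fix it, so it is an assumption. Uncovered days = 28 − d.

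| Assumed exit | Uncovered of 28 |
|---|---|
| Dosing day, d = 0 | 28 |
| One day later, d = 1 | 27 |
| One week later, d = 7 | 21 |

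If the contact required by note g takes place and AE collection continues to it, no days are uncovered.

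**The case against.** The strongest reply is that the protocol already requires this follow-up elsewhere. 8.3.1 covers each participant and does not shorten the window for those who stop because of an AE. 8.3.3 and Appendix 3 require events to be pursued, and note g makes the contact mandatory. 7.1 itself leads to the early-termination visit, which includes physical examination, safety laboratory tests, ECG, vital signs, a PK sample and AE monitoring. In a single-dose crossover, 7.1 may mean only that the participant receives no further periods and gives no further PK data. The stated half-life is 2 to 3 hours, and confinement runs to the 24-hour sample, so the period of highest exposure is observed in-house for anyone who does not leave early.

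Much of this stands. It rules out saying that safety follow-up is lost by design. It does not remove the conflict: the narrower meaning of 7.1 is not what the sentence says, and the release in 8.3.1 gives a site a good-faith reason to stop.

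Four stronger readings are tempting, and the documents do not support them:

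- **That participants stopped for safety are followed less than those who stop by choice.** 8.3.1 and note g apply to both groups.
- **That 7.1 deals only with safety stops.** Its reasons are introduced as a list that includes these two, so it is not exhaustive.
- **That 7.2 is a further contradiction.** The sentence "The participant will be permanently discontinued from the study intervention and the study at that time" concerns withdrawal from the study, where that result is ordinary, and the same section refers to the SoA for follow-up assessments.
- **That the dropout allowances measure the problem.** The 6 of 36 in Cohort 1 and 4 of 36 in Cohort 2 (Protocol 9.5) cover dropouts in general, and neither document gives a rate of stopping for safety.

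**Conclusion.** Section 7.1 is wrong as written, as a matter of wording. Its unqualified sentence cannot stand beside the 28-day minimum in 8.3.1, the mandatory contact in SoA note g and the follow-up duty in 8.3.3, and it is opposed in wording to 7.2.1.

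The consequence is a risk of inconsistent site practice. For a participant handled under the literal reading, about 27 of the 28 required collection days would be uncovered if exit comes one day after the last dose, with a range of 21 to 28 days for exit between day 7 and the dosing day. This rests on the assumed exit day and on the site treating 7.1 as ending participation. How many participants would be affected cannot be estimated from the documents.

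The point concerns safety data and participant oversight only. The bioequivalence model, the confidence intervals, the acceptance limits, the power and the sample size do not depend on it.

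**What to change.** Reconcile the 7.1 sentence with 7.2.1, 8.3.1, 8.3.3 and the SoA, so that all of them give one participant status and one safety-collection window after dosing stops. State explicitly whether 7.1 ends only further dosing and PK evaluation or also AE collection. If it is meant to end AE collection too, 8.3.1 and note g would have to say so, because at present they do not allow it.

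The stopping criteria are not part of this change. The cost is a protocol wording amendment. No visit needs to be added, because the early-termination visit and the follow-up contact are already scheduled and the contact may be by telephone. The sample size and the bioequivalence analysis stay as they are.
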